#### 4.4.5 Method of Assigning Subjects to Treatment Groups

Subjects will be randomized to either Exufiber® (6w) or to Aquacel® Extra (6w). At least 50 out of the total 212 subjects will be randomized to Exufiber® (24w) or to Aquacel® Extra (24w). The randomization will be centralized performed after cleansing/debridement using an electronic system using the minimization technique and with the following strata; Wound duration (6w-12m,>12m), wound area (<10cm^2,≥10cm^2), ABPI (0.7-0.9,>0.9), Compression at inclusion (No, Yes) ( Margolis, 2004 (2)).

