## **4.8 Statistical Methods and Determination of Sample Size**

### **4.8.1 Statistical Evaluation**

The intent-to-treat (ITT) population is defined as all randomised patients with at least one follow up planimetry value (from the validated tool PictZar) and the per-protocol (PP) population as all patients with a wound area measurement till the fourth week of follow-up, at least. Subjects with significant protocol deviations will be excluded from the PP population.

PictZar has received 510k notification and is compliant with CFR Part 11.

In this non-inferiority study the primary efficacy analysis will be constructing a two sided 95% confidence interval, using Fisher's non-parametric permutation test, for between-treatment differences (Exufiber® - Aquacel® Extra) in the mean percentage area change from baseline to 6 weeks. This means that if the lower limit of this confidence interval is greater than 12% non-inferiority will be established.

All the main efficacy analyses will be performed on the PP population. Complementary efficacy analyses will be performed on the ITT-population for further confirmation. The ITT and PP analyses will have to provide the same results to establish the non-inferiority. All safety analysis will be performed on the safety population.

Superiority can be concluded if the lower bound of a two sided 95% confidence interval for between-treatment differences (Exufiber® - Aquacel® Extra) in the mean percentage area change from baseline to 6 weeks does not overpass zero.

There will also be a second blinded assessment carried out (not using the PictZar system) that will support the main analysis done by PictZar.

For secondary variables Fishers exact test for dichotomous variables, Mantel-Haenszel chi-square test for ordered categorical variables and Pearson Chi-square test for non-ordered categorical variables and Fisher's non-parametric permutation will be used for continuous variables.

If necessary adjustment for baseline variables will be done with multiple logistic regression for dichotomous variables and with covariance analysis for continuous variables.

All statistical tests will be two-sided and conducted at the 5% significance level.

A sub-group analysis by country will be performed.

For the primary endpoint last observation carried forward will be applied for the final measurement. No other imputation methods will be used.

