**Title: CIP with integrated Central Amendment 1, 2, 3 and 4**

Page 37(42)

**Investigation Code Chexu03****Final Version CIP Approval date 2016-04-19****Amendment 1 Approval date 2016-10-17****Amendment 2 Approval date 2016-12-19****Amendment 3 Approval date 2017-09-12****Amendment 4 Approval date 2017-12-28**

Inclusion completed: Estimated Q1/Q2 2019

Last subject out: Estimated Q3 2019

The investigation could be prematurely discontinued if the dropout rate is higher than 20% and/or the investigation site is unable to fulfill the inclusion period according to the Clinical Investigation Agreement.

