## **5. VARIABLES OF ANALYSIS**

### **5.1 Subjects Characteristics**

- Age
- Gender
- Race (where applicable)
- Mobility
- Height, weight and BMI (calculated)
- Duration of leg ulcer and wound location
- Latest ABPI value
- Recurrent ulcer
- Current dressing and current compression

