## 6. STATISTICAL METHODOLOGY AND SAMPLE SIZE DETERMINATION

### 6.1 General Methodology

In this non-inferiority study the primary efficacy analysis will be constructing a two sided 95% confidence interval, using Fisher's non-parametric permutation test, for between-treatment differences (Exufiber® - Aquacel® Extra) in the mean percentage wound area reduction from

baseline to 6 weeks follow-up. This means that if the lower limit of this confidence interval is greater than 12% non-inferiority will be established.

All the main efficacy analyses will be performed on the PP population. Complementary efficacy analyses will be performed on the ITT population for further confirmation. The ITT and PP analyses will have to provide the same results to establish the non-inferiority. All safety analysis will be performed on the safety population.

Superiority can be concluded if the lower bound of a two sided 95% confidence interval for between-treatment differences (Exufiber® - Aquacel® Extra) in the mean percentage wound area reduction from baseline to 6 weeks follow-up does not overpass zero.

There will also be a second blinded assessment carried out by an independent French expert (not using the PictZar system) that will support the primary efficacy analysis done by PictZar.

For comparison between the two randomized groups regarding baseline variables and secondary efficacy variables Fisher's non-parametric permutation will be used for continuous variables, Mantel-Haenszel chi-square test for ordered categorical variables, Pearson Chi-square test for non-ordered categorical variables and Fishers exact test will be used for dichotomous variables.

For continuous variables 95% confidence intervals based on Fisher's non-parametric permutation tests will be calculated for the mean differences between the two groups. For dichotomous variables 95% confidence intervals for difference in proportion will be calculated.

If significant differences are found in baseline variables between the two treatments, complementary analyses of treatment adjusted for these baseline variables will be performed. These adjustments for baseline variables will be done with multiple logistic regression analyses for dichotomous variables and with covariance analysis for continuous variables.

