## **6.2 Demographics and Baseline Characteristics**

The variables listed in section 5.1 and 5.2 will be described and analyzed between the two treatment groups according to the general methodology in section 6.1 above. These analyses and tables will be given for both the ITT and PP population.

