## **6.3 Efficacy Analyses**

### **6.3.1 Primary efficacy analysis**

In this non-inferiority study the primary efficacy analysis will be constructing a two sided 95% confidence interval, using Fisher's non-parametric permutation test, for between-treatment differences (Exufiber® - Aquacel® Extra) in the mean percentage wound area reduction from baseline to 6 weeks follow-up using PictZar on the PP population. A corresponding complementary two sided 95% confidence interval on the ITT population will also be constructed. If the lower limits of both these confidence intervals are greater than 12% non-inferiority will be established.

For the primary efficacy endpoint last observation carried forward will be applied for the last follow-up measurement before 6 weeks and forward to the final 6 week measurement. Supporting identical analyses will be performed on the primary efficacy variable using the values from a second supportive blind review of the independent French expert.

Also a sensitive analysis using PictZar will be performed using complete cases.

Tables will be given for wound area by visit and analysed between treatments and for wound area reduction (%) from baseline to each visit and analysed between treatments.

Superiority can be concluded if the lower bound of a two sided 95% confidence interval for between-treatment differences (Exufiber® - Aquacel® Extra) in the mean percentage wound area reduction from baseline to 6 weeks follow-up using PictZar on the ITT population does not overpass zero.

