## 6.5 Determination of Sample Size

This investigation was designed to document the non-inferiority of the test dressing, Exufiber®, compared with the control dressing, Aquacel® Extra, on the relative reduction/change in wound size from baseline to end of investigation (6w). Applying a non-inferiority margin of 12% (same as EARTH investigation, Meaume et al 2014) and a standard deviation of 35%, 106 subjects were necessary in each group (i.e. 212 subjects in total) with

a power level at 80%. Two investigations have previously been conducted on Exufiber®, one on diabetic foot ulcer and one on pressure ulcer. The SD are a little higher than 35% but since those investigations were quite small (21 subjects) it is reasonable to expect a smaller SD which justifies the calculation above.

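### Allocation is minimised on four factors but the primary interval has no term for them, so it is conservative and gives up precision if they predict healing

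*SAP*

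**What the plan says.** Protocol 4.4.5 describes central allocation by "an electronic system using the minimization technique and with the following strata; Wound duration (6w-12m,>12m"; the other factors are wound area (below 10 cm² or not), ABPI (up to 0.9 or above) and compression at inclusion (no or yes). The list of factors carries a citation that Protocol section 7 identifies as a study of prognostic models for venous leg ulcers.

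SAP 6.1 and 6.3.1 and Protocol 4.8.1 base the primary analysis on a two-sided 95% interval for the difference in mean percentage area reduction, obtained from Fisher's permutation test. No covariate or stratum enters it. The PP and ITT intervals decide the result together: "If the lower limits of both these confidence intervals are greater than 12% non-inferiority will be established". (The margin is printed without a minus sign; it is read here as −12.)

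SAP 6.1 deals with adjustment as follows: "If significant differences are found in baseline variables between the two treatments, complementary analyses of treatment adjusted for these baseline variables will be performed". Protocol 4.8.1 is looser: "If necessary adjustment for baseline variables will be done with multiple logistic regression", with covariance analysis for continuous outcomes. The between-group baseline tests that feed the SAP trigger cover the SAP 5.1 list, including "Duration of leg ulcer and wound location" and ABPI, and SAP 6.2 says "These analyses and tables will be given for both the ITT and PP population". The between-group test of wound area comes from SAP 6.3.1, which analyses area at each visit. Neither document names the minimisation factors as covariates in any analysis, and the SAP does not mention minimisation.

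**The concern.** Minimisation keeps the arms nearly equal on the four factors. A plain permutation test takes its reference distribution from all re-allocations, including those with imbalances that minimisation would have prevented. If the factors explain part of the variation in healing, that distribution is too wide, and so is the interval. The balance bought at allocation is then not used in the analysis.

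The adjustment rule does not repair this, for two reasons. The adjusted result is supplementary, so it cannot change the non-inferiority decision. The trigger also chooses covariates by chance imbalance, and minimisation makes significant imbalance on these factors very unlikely. The protocol's looser condition is undefined, which leaves the choice of covariates open in an open-label trial.

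At stake is the chance that a truly non-inferior dressing is shown to be so, in a trial that must succeed in both populations.

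**Working it through.** **Inputs from the documents.** Margin 12 and power 80% (SAP 6.5); "a standard deviation of 35%, 106 subjects were necessary in each group" (SAP 6.5); two-sided 95% interval (SAP 6.1, 6.3.1). **Assumptions.** True difference 0. R², the share of outcome variance explained by the four factors, is not in the documents and is varied from 0 to 30%.

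**1. The plan's own figure.** n per arm = 2(z₁₋α + z₀.₈₀)² × 35²/12².
- One-sided 5%: 2 × (1.645 + 0.842)² × 1225/144 = 105.2, so 106. This reproduces the plan.
- One-sided 2.5%, which matches the specified interval: 2 × (1.960 + 0.842)² × 1225/144 = 133.5, so 134.

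The trial therefore starts from about 70% power. That is a separate sizing issue.

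**2. Normal approximation with near-perfect balance.** SE = 35 × √(2/106) = 4.81 and the unadjusted half-width is 1.96 × 4.81 = 9.42. The difference in means actually varies with SE × √(1 − R²).
- ANCOVA half-width: 9.42 × √(1 − R²)
- ANCOVA power: Φ(12/[4.81√(1 − R²)] − 1.96)
- Unadjusted power: Φ((12 − 9.42)/[4.81√(1 − R²)])
- Unadjusted one-sided error at the margin: 1 − Φ(1.96/√(1 − R²))

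| R² | ANCOVA half-width | Unadjusted power | ANCOVA power | Unadjusted error |
|---|---|---|---|---|
| 0 | 9.42 | 70.4% | 70.4% | 2.5% |
| 5% | 9.18 | 70.9% | 72.6% | 2.2% |
| 10% | 8.94 | 71.4% | 74.9% | 1.9% |
| 20% | 8.43 | 72.6% | 79.7% | 1.4% |
| 30% | 7.88 | 73.9% | 84.7% | 1.0% |

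**3. Simulation with minimisation.** 100,000 trials of 212 subjects. Assumed: biased coin 0.8; factor prevalences 0.42, 0.55, 0.67 and 0.60; equal contribution of each factor to R². Intervals are t-based. Monte Carlo error is about 0.15 points on power.

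| R² | Unadjusted power | ANCOVA power | Unadjusted error | Unadjusted coverage | ANCOVA half-width |
|---|---|---|---|---|---|
| 0 | 70.0% | 70.0% | 2.4% | 95.0% | 9.5 |
| 5% | 70.4% | 72.1% | 2.2% | 95.6% | 9.2 |
| 10% | 70.9% | 74.4% | 1.9% | 96.1% | 9.0 |
| 20% | 71.9% | 79.3% | 1.4% | 97.1% | 8.5 |
| 30% | 73.1% | 84.3% | 1.0% | 97.9% | 7.9 |

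The unadjusted half-width is 9.5 and the ANCOVA error 2.4% throughout. An actual permutation test (2,000 trials, 1,000 permutations each) gave power of 70.6, 70.7 and 72.2% at R² 10, 20 and 30%, against 70.4, 71.1 and 72.3% for the t interval, so the t interval is a fair stand-in.

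**4. Variations.**
- *Both populations must succeed.* With 10% of subjects randomly outside PP (assumed): 63.2 against 67.4% at R² 10%, and 63.8 against 72.7% at R² 20%. With 20% outside: 57.4 against 61.6%, and 57.8 against 67.1%. The 20% is borrowed from Protocol section 6: "The investigation could be prematurely discontinued if the dropout rate is higher than 20" per cent. It is a stopping threshold, used only as an upper bound.
- *Outcome capped at its upper end (about 21% at the cap):* 70.5 against 74.1% at R² 10%, and 71.5 against 79.0% at R² 20%.
- *Signal in continuous log area, log duration and ABPI (20,000 trials):* unadjusted 70.8 and 71.4% at R² 10 and 20%; ANCOVA on the categories 73.5 and 76.8%; ANCOVA on the continuous values 74.6 and 79.5%.

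**5. The trigger.** A significant difference on any categorised factor arose in 4 of 100,000 trials (0.08% in a random 80% PP subset). On continuous duration, area or ABPI it arose in 1.7% (3.3% in that subset).

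**6. R² needed to restore 80% power.** From step 1, 1 − 106/133.5 = 0.206; the noncentral t gives 0.214. This applies when the signal lies in the categories.

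**The case against.** The strongest reply is that nothing invalid happens. The method is pre-specified, the same in protocol and SAP, keeps the error at or below 2.5%, and makes few assumptions about an outcome that is bounded above while wounds can also enlarge. That is correct, and it is why this is a question of efficiency. The bounded outcome does not weaken the case for ANCOVA: under a cap the gain is almost unchanged.

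Secondly, R² is unknown and may be small. The endpoint is already relative to baseline area, and all subjects should receive compression during the trial whatever they had at inclusion. This stands: the gain is nil at R² = 0 and about 1.7 points at 5%. The plan does, however, balance on these factors with a prognostic-model citation, and including them at R² = 0 costs nothing visible (half-width 9.5 either way).

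Thirdly, the larger gains assume that the signal lies in the categories. With continuous signal the gain from categorical adjustment is 2.7 points at R² 10% and 5.4 at 20%, and R² of about 0.21 would not restore 80% power. This also stands. The trigger frequencies likewise depend on assumed prevalences and coin probability, and show only that triggering is rare.

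Finally, the protocol says the SAP would be final before the first subject entered, the trial is open-label, and sponsor staff can view entered data. A late change of primary analysis therefore carries some cost in credibility. An adjusted sensitivity analysis would avoid that cost, but it would leave the deciding interval as wide as before.

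**Conclusion.** The concern holds. Four factors govern allocation, none enters the intervals that decide non-inferiority, and the adjustment rule neither reaches that decision nor is likely to select those factors. To the extent that they predict healing, the primary interval is conservative.

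The power gain from ANCOVA is nil at R² = 0, about 1.7 points at 5%, 3.5 at 10%, 7.4 at 20% and 11.2 at 30%, and smaller if the signal is continuous. These figures rest on an assumed R², SD 35, a true difference of 0, a margin read as −12 and assumed factor prevalences. The direction does not depend on the exact values. The change should be made, but the existing analysis would not produce excess false claims without it. The fall from 80% to about 70% power has a different cause and needs its own correction.

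**What to change.** Pre-specify as primary, in both PP and ITT, an ANCOVA of percentage wound area reduction on treatment and the four factors, categorised as in Protocol 4.4.5: duration up to or over 12 months, area below or at least 10 cm², ABPI 0.7–0.9 or above 0.9, compression at inclusion no or yes. Use the values entered at randomisation, and say so, because the central PictZar baseline area may fall on the other side of 10 cm². Compare the two-sided 95% interval for the adjusted difference with the non-inferiority margin. If a design-based method is preferred, use a re-randomisation test that reproduces the minimisation. Keep the unadjusted permutation interval as a sensitivity analysis. Delete the significance trigger in SAP 6.1, and replace the undefined condition in Protocol 4.8.1 with the same covariate list.

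No new data are needed, since the allocation system requires all four values. The cost is a SAP revision and a few lines of SAS, dated and justified before database lock, plus a protocol amendment, which under Protocol 4.9 may need ethics committee or authority notification or approval.

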For the primary efficacy endpoint, and for applicable secondary efficacy endpoints, last observation carried forward will be applied for the last follow-up measurement before 6 weeks and forward to the final 6 week measurement. No other imputation methods will be used.

For the primary efficacy endpoint a sensitivity analysis will be performed using complete case.

Frequency tables (including n, mean, median, standard deviation, minimum and maximum for continuous variables and n, frequency and percentage for categorical values) will be provided for all variables by treatment, as well as for the changes from baseline within each treatment by treatment.

Sub-group analyses by country will be performed.

Exploratory interaction analyses will be performed for primary efficacy variable and selected secondary variables between study groups and selected baseline variables in order to find subgroups where the effect of Exufiber in relation to Aquacel Extra is significantly improved. All statistical tests will be two-sided and conducted at the 5% significance level. All analysis will be performed with SAS software version 9.4 or later.

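### SAP 6.1 picks covariates for the supportive adjusted analyses by baseline p-value, so they will often be chance picks and almost never the four factors used for minimisation

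*SAP*

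**What the plan says.** The rule is in SAP 6.1: "If significant differences are found in baseline variables between the two treatments, complementary analyses of treatment adjusted for these baseline variables will be performed". The same section fixes the level for the tests that feed it: "All statistical tests will be two-sided and conducted at the 5% significance level". No allowance for multiple baseline tests is described.

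SAP 6.2 sets out what is tested at baseline: "The variables listed in section 5.1 and 5.2 will be described and analyzed between the two treatment groups". It then adds: "These analyses and tables will be given for both the ITT and PP population". It does not say which of the two sets triggers the adjustment, or what happens if they disagree.

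Protocol 4.8.1 is looser: "If necessary adjustment for baseline variables will be done with multiple logistic regression for dichotomous variables", with covariance analysis for continuous variables. It names no covariate and gives no criterion.

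Protocol 4.4.5 describes central allocation "using the minimization technique and with the following strata; Wound duration (6w-12m,>12m), wound area", followed by ABPI and compression at inclusion. The SAP mentions neither minimisation nor these four factors as covariates. The primary interval in SAP 6.3.1 is unadjusted.

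**The concern.** Adjustment is useful when a covariate predicts the outcome. A between-arm p-value at baseline measures something else: how far the arms happen to differ. A variable with no bearing on healing enters the model if it reaches p<0.05, while a strongly prognostic one at p=0.06 stays out.

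Minimisation makes this worse. The sponsor chose four factors as important enough to balance, and balancing them removes the signal the trigger looks for. The rule is therefore least likely to adjust for the variables the design itself singles out.

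At stake is the value of the supportive analysis. Its covariates are unknown until the arms are compared, could differ between PP and ITT, and would differ by chance if the trial were repeated.

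**Working it through.** **Reference figure.** The documents give no figure for this rule. The sample size is used below only to set the scale. With margin 12, SD 35 and 80% power, n per group = 2(z_α + z_β)²(SD/margin)².
- One-sided 5%: 2(1.645 + 0.842)²(35/12)² ≈ 105.2, so 106, matching SAP 6.5.
- One-sided 2.5%, matching the planned two-sided 95% interval: 134.

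That mismatch is a separate matter. It explains why the power baseline in step 4 is 70.4% and not 80%.

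**Step 1: count the tests.** SAP 5.1 gives 13 variables when height, weight and BMI are counted separately: age, gender, race, mobility, height, weight, BMI, ulcer duration, wound location, ABPI, recurrence, current dressing and current compression. Duration, ABPI and compression are minimisation factors, leaving 10. SAP 5.2 adds two (medical conditions, surgical history), making 12.

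**Step 2: chance of at least one chance trigger.** For k independent tests at 5% this is 1 − 0.95^k.

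| k | Chance | Expected number |
|---|---|---|
| 10 | 1 − 0.95^10 = 40.1% | 0.5 |
| 12 | 1 − 0.95^12 = 46.0% | 0.6 |

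Simulation with 12 independent variables gave 44% to 48%. Race is tested only where applicable. Without it, k is 9 or 11, giving 37.0% or 43.1%. Correlation among height, weight and BMI lowers the figures somewhat.

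**Step 3: how often minimised factors trigger.** Monte Carlo of minimisation on four binary factors, N = 212, 1,500 to 2,000 runs per setting. The documents do not state the assignment probability, so 0.8 and 1.0 were assumed. Categories were tested with Fisher's exact test. Continuous values were tested with a t-test standing in for the permutation test. Covariate distributions are assumed.

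| Setting | At least one significant |
|---|---|
| Four categories, minimised | 0% |
| Four categories, simple randomisation | 14.8% |
| Continuous duration, area or ABPI, normal shape | 0.2% to 0.8% |
| Continuous, area and duration skewed | 2.1% to 2.3% |
| Categories after 20% random exclusion (PP-like, probability 0.8) | 0.07% |
| Continuous, skewed, after the same exclusion | 4.5% |

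**Step 4: what a fixed list could add.** Adjusting for covariates that explain a share R² of outcome variance reduces the SD to 35√(1 − R²). At 106 per arm, true difference 0 and a two-sided 95% interval, power = Φ(12/(SD√(2/106)) − 1.96).
- Unadjusted: 12/4.81 − 1.96 = 0.54, so 70.4%.
- R² = 0.1, 0.2, 0.3: 74.9%, 79.7%, 84.7%.

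The R² values are assumptions; the documents give none. The gain would apply to the supportive interval only.

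**Step 5: does the rule damage coverage?** The two-stage rule was simulated with 106 per arm, 10 independent normal covariates, simple 1:1 allocation, SD 35, R² from 0 to 0.3 and 20,000 runs per setting. The trigger rate was 40%. Overall coverage was 95.0% to 95.7%, and a repeat simulation gave 95.4% to 95.9%. Among triggered runs the adjusted interval covered 94.9% to 95.8% and the unadjusted interval 93.8% to 94.9%. Taking the margin as −12 and the true difference as 0, adjusted and unadjusted non-inferiority verdicts differed in 5% to 12% of triggered runs, or 2% to 5% of all runs.

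**The case against.** The strongest reply is that nothing decisive rests on this rule. SAP 6.1 calls the adjusted analyses complementary, and SAP 6.3.1 bases non-inferiority on the unadjusted PP and ITT intervals. A 40% chance of running one more supportive model is not in itself a harm. This stands, and it limits the weight of the point.

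A reader might go further than the documents allow in four ways.

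- **That intervals lose their nominal coverage after such selection.** Selection uses baseline data and arm, not outcome, and step 5 shows no material loss.
- **That the rule cannot adjust for the minimisation factors.** Duration, ABPI and compression are listed in SAP 5.1 and tested, so they can trigger. They will simply almost never do so.
- **That baseline wound area escapes comparison because SAP 5.1 and 5.2 omit it.** SAP 6.3.1 plans tables of wound area by visit, analysed between treatments, and the trigger sentence refers to baseline variables generally.
- **That every significant imbalance is chance.** That is exact only for the full randomised set. ITT requires a follow-up measurement. PP requires a week-6 area (or earlier healing) and no significant violations. Both sets are formed after randomisation in an open trial, so imbalance there may be systematic. A p-value trigger does not handle that well either.

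It can also be said that the protocol contains no p-value trigger and leaves detail to the SAP. That is true, but its open condition names no covariate and so gives the SAP no better rule to follow.

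**Conclusion.** The point holds as a weakness in a stated method for supportive analyses. The rule has about a 40% to 46% chance of bringing in at least one variable through chance imbalance, assuming 10 to 12 independent tests at 5%. It will almost never bring in the four minimisation factors: 0% for their categories in the randomised set, and up to 4.5% for continuous versions in the least favourable setting tried. That result rests on assumed assignment probabilities and covariate distributions. The SAP also leaves open whether ITT or PP triggers the adjustment.

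The formal non-inferiority decision is unaffected. A supportive verdict that conflicts with the primary one is possible but uncommon, at 2% to 5% of all runs under the step 5 assumptions. What is lost is pre-specification, together with the precision a prognostic covariate set could give the supportive interval. The size of that gain depends on an R² the documents do not provide.

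**What to change.** 1. In SAP 6.1, delete the sentence that makes adjustment depend on significant baseline differences.
2. In its place, state that a supportive covariance analysis (logistic regression for dichotomous outcomes), adjusted for wound duration, wound area, ABPI and compression at inclusion, is always run in both PP and ITT, whatever baseline differences are observed. Enter area and duration preferably as continuous variables. These four are the documents' own list of factors.
3. In protocol 4.8.1, replace the open condition on adjustment with a reference to that fixed list.
4. In SAP 6.1 and 6.2, keep the baseline tables descriptive, without between-arm tests. This also removes the question of which population triggers.

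The primary unadjusted interval need not change for this point to be resolved. The cost is wording in two documents and one extra supportive analysis, with fewer baseline tests and no new data.
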